4.9.3 Laboratory Data

Clinical laboratory evaluations include:

Hematology: hemoglobin, hematocrit, red blood cell count, white blood cell count with differential, and platelets

Serum Chemistry: sodium, potassium, chloride, bicarbonate, calcium, glucose, BUN (urea), serum creatinine, uric acid, ALT, AST, alkaline phosphatase, LDH, total protein, albumin, total bilirubin, direct bilirubin, indirect bilirubin, CPK (with fractionation, if available)

Lipid Panel: Cholesterol, LDL, HDL, triglycerides (screening only)

Estimated glomerular filtration rate (eGFR) using the estimated modification of diet in renal disease (MDRD) formula will be calculated and reported by the central lab at each visit that the clinical laboratory test is collected.

Urinalysis: pH, specific gravity, protein, ketones, nitrites, urobilinogen, leukocyte esterase, protein, glucose, microalbuminuria, and blood. If blood, protein, or leukocytes are positive, reflex to microscopic examination.

Urine drug screen: for drugs of abuse

Clinical laboratory values will be expressed using both Standard US units and SI units. Tabulations, listings, and graphics will be provided to show the data in both systems, unless specified otherwise.

The observed value and change from baseline will be summarized for select continuous laboratory parameters at baseline and the end of treatment visit. In addition, the shift from baseline in laboratory tests will be summarized as the number and percentage of subjects with each category (low, normal, high) at baseline and the end of treatment visit. Note that shift

categories are independent of US and SI units. For AST and ALT, the shift tables will use the following categories (SI and US units are the same): Normal, >ULN, >3x ULN, and >5x ULN. In the event of repeat values from the same post-baseline visit, the non-missing value closest to the target date for the visit will be used. In the case of a tie, the latest record will be used.

All laboratory data will be provided in by-subject listings that indicate which values are on study or on treatment. Additional listings will be presented for all abnormal laboratory values.

On-study laboratory values are those with collection date/time after the randomization date/time.

On-treatment laboratory values are those with collection date/time after the first dose of study drug date/time. (Thus, on-treatment laboratory values are a subset of on-study values.)

These definitions of on-study/on-treatment apply to vital signs, physical measurements, ECGs, and suicidal ideation and behaviors.

4.9.3.1 *Liver Toxicity Evaluation*

Potential drug induced liver injury (DILI) are those events meeting Hy's Law, defined as:

1. Aminotransferases (AT) ALT or AST elevation > 3 times the upper limit of normal (ULN);
2. Total bilirubin (TBL) > 2 times ULN, without initial findings of cholestasis (elevated serum alkaline phosphatase); and
3. No other immediately apparent possible causes of AT elevation and hyperbilirubinemia, included but not limited to: viral hepatitis, pre-existing chronic or acute liver disease, or the administration of other drug(s) known to be hepatotoxic.

Any on-study potential DILI, meeting the above defined criteria, will be reported as SAEs in the SAE summary table (see [Section 4.9.2](#)). A by-subject listing of potential DILI will be prepared that shows the AT and TBL values for all subjects that experience either AT > 3 times the upper limit of normal or TBL > 2 times the upper limit of normal at any time.

Additionally, a table will be created that summarizes the on-study incidence (as the number and percentage of subjects with an elevation) of the following:

- >3x, >5x, >10x, and >20x ULN elevations of AST, ALT, and either ALT or AST
- Any elevations of bilirubin >1x ULN and >2x ULN
- Any elevations of ALP > 1.5x ULN
- Elevation of AST or ALT (>3x ULN) accompanied by elevated bilirubin (>1.5x ULN and >2x ULN)

- Elevation of AST or ALT along with an on-study AE of nausea, vomiting, anorexia, abdominal pain, or fatigue

An evaluation of on-study Drug-Induced Serious Hepatotoxicity (eDISH) plot will be created by plotting the maximum total bilirubin against maximum ALT and presenting these data points by treatment group. The maximum values for each subject during the study will be identified as the maximum values that occur on study, but not necessarily concurrently. Maximum total bilirubin (presented as xULN) will be plotted on a log scale on the y-axis and maximum ALT (presented as xULN) will be plotted on a log scale on the x-axis. A horizontal reference line will be placed at 2x ULN for maximum total bilirubin, and a vertical reference line will be placed at 3x ULN for maximum ALT. The lower left quadrant will be labeled “Normal Range”. The upper left quadrant will be labeled “Hyperbilirubinemia”. The lower right quadrant will be labeled “Temple’s Corollary”. The upper right quadrant will be labeled “Possible Hy’s Law Range”.

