1.2.4 Clinical Adverse Event Profile

Rimegepant appears to be generally safe and well tolerated in humans when given as single oral doses up to the maximum dose of 1500 mg and multiple oral doses up to the maximum daily dose of 600 mg for 14 days. Please refer to the current version of Investigators Brochure for a summary of the clinical safety profile.

The primary identified AE of interest is potential change in liver function tests. Investigators must carefully monitor routine liver function tests (ALT, AST, total bilirubin, and ALP) and potentially liver related symptoms and signs. Clinicians should also monitor changes in hematology and other laboratory measures. Please refer to the current Investigators Brochure for further information regarding the clinical safety profile of rimegepant.

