8.2.2 Laboratory Test Abnormalities

The following laboratory test abnormalities should be captured on the non-serious AE CRF page or SAE Report Form (paper or electronic) as appropriate:

1. Any laboratory test result that is clinically significant or meets the definition of an SAE;
2. Any laboratory abnormality that required the subject to have the study drug discontinued or interrupted;
3. Any laboratory abnormality that required the subject to receive specific corrective therapy.

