1.2.3 Exploratory Objectives

1. To evaluate the effect of rimegepant relative to placebo on the subjects’ ability to work or function at 24 hours post-dose according to the FDS.

2. To evaluate the effect of rimegepant compared to placebo on pain relief at 30 minutes post-dose.
3. To evaluate the effect of rimegepant compared to placebo on pain relief at 15 minutes post-dose.
4. To evaluate the effect of rimegepant relative to placebo on the Migraine Preference of Medication (PoM).
5. To evaluate rimegepant relative to placebo for pain relief on the 4-point scale at all scheduled time points post-dose.
6. To evaluate the effect of rimegepant relative to placebo on the Migraine Quality of Life Questionnaire (MQoLQ).
7. To evaluate the tolerability and safety of rimegepant in the acute treatment of migraine as measured by the frequency of adverse events of at least moderate intensity, serious adverse events, and clinically relevant laboratory abnormalities.
8. To evaluate the effect of rimegepant (75 mg ODT) relative to placebo on the Sheehan Suicidality Tracking Scale (S-STs).

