14.2.3.8	Freedom from Most Bothersome Symptom at Every Timepoint Post Dose: Exploratory Analysis	mITT Subjects	Y
14.2.3.9	Freedom from Photophobia at Every Timepoint Post Dose: Exploratory Analysis	mITT Subjects	
14.2.3.10	Freedom from Phonophobia at Every Timepoint Post Dose: Exploratory Analysis	mITT Subjects	

Table Number	Title	Population	Topline
14.2.3.11	Freedom from Nausea at Every Timepoint Post Dose: Exploratory Analysis	mITT Subjects	
14.2.3.12	Functional Disability Scale at Every Timepoint Post Dose: Exploratory Analysis	mITT Subjects	Y
14.2.3.13.1	Kaplan-Meier Time to First Report of Pain Freedom up to 8 Hours Post Dose: Exploratory Analysis	mITT Subjects	Y
14.2.3.13.2	Median Time to First Report Pain Freedom: Exploratory Analysis	mITT Subjects	Y
14.3.1.1	Self-Reported Study Drug Exposure Summary	All Randomized Subjects who had a Study Migraine	
14.3.1.2	Study Drug Accountability Summary	All Randomized Subjects who had a Study Migraine	
14.3.1.3	Cross Tabulation of Study Drug Exposure and Accountability	All Randomized Subjects who had a Study Migraine	
14.3.2.1	Summary of On-Study Adverse Events	Treated Subjects	Y
14.3.2.2	Incidence of On-study Adverse Events by System Organ Class and Preferred Term	Treated Subjects	Y
14.3.2.3	Incidence of On-study Adverse Events Related to Study Drug by System Organ Class and Preferred Term	Treated Subjects	
14.3.2.4	Incidence of On-study Serious Adverse Events by System Organ Class and Preferred Term	Treated Subjects	Y
14.3.2.5	Incidence of On-study Adverse Events with Severe Grade by System Organ Class and Preferred Term	Treated Subjects	Y
14.3.2.6	Incidence of On-Study Adverse Events Leading to Study Drug Discontinuation by System Organ Class and Preferred Term	Treated Subjects	
14.4.1.1	Hematology (SI Units): Observed and Change From Baseline Values by Visit	Treated Subjects	
14.4.1.2	Hematology (UI Units): Observed and Change From Baseline Values by Visit	Treated Subjects	
14.4.2.1	Serum Chemistry (SI Units): Observed and Change From Baseline Values by Visit	Treated Subjects	
14.4.2.2	Serum Chemistry (US Units): Observed and Change From Baseline Values by Visit	Treated Subjects	
14.4.3	Hematology: Shift from Baseline by Visit	Treated Subjects	
14.4.4	Serum Chemistry: Shift from Baseline by Visit	Treated Subjects	
14.4.5	Urinalysis: Shift from Baseline by Visit	Treated Subjects	
14.4.5.2	Urine Drug Screen: Shift from Baseline by Visit	Treated Subjects	

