16.2.7.4	Adverse Events Leading to Study Drug Discontinuation	Treated Subjects	
16.2.8.1.1	Hematology Results (SI Units)	Enrolled Subjects	
16.2.8.1.2	Hematology Results (US Units)	Enrolled Subjects	
16.2.8.2.1	Serum Chemistry Results (SI Units)	Enrolled Subjects	
16.2.8.2.2	Serum Chemistry Results (US Units)	Enrolled Subjects	
16.2.8.2.3	CK and Fractionation Results (SI Units)	Enrolled Subjects	
16.2.8.2.4	CK and Fractionation Results (US Units)	Enrolled Subjects	
16.2.8.3.1	Urinalysis Results (SI Units)	Enrolled Subjects	
16.2.8.3.2	Urinalysis Results (US Units)	Enrolled Subjects	
16.2.8.3.3	Urine Drug Screen Results	Enrolled Subjects	
16.2.8.4.1	Endocrine Results (SI Units)	Enrolled Subjects	
16.2.8.4.2	Endocrine Results (US Units)	Enrolled Subjects	
16.2.8.5.1	Pregnancy Test Results (SI Units)	Enrolled Subjects	
16.2.8.5.2	Pregnancy Test Results (US Units)	Enrolled Subjects	
16.2.8.6	GC/MS Results	Enrolled Subjects	
16.2.8.7.1	All Abnormal Laboratory Results (SI Units)	Enrolled Subjects	
16.2.8.7.2	All Abnormal Laboratory Results (US Units)	Enrolled Subjects	
16.2.8.8.1	Potential Drug Induced Liver Injury (SI Units)	Enrolled Subjects	
16.2.8.8.2	Potential Drug Induced Liver Injury (US Units)	Enrolled Subjects	
16.2.9.1	Vital Signs and Physical Measurements	Enrolled Subjects	
16.2.9.2	Electrocardiogram Results	Enrolled Subjects	
16.2.9.3.1	Non-Study Medications	Enrolled Subjects	
16.2.9.3.2	Non-Study Prophylactic Migraine Medications	Enrolled Subjects	
16.2.9.3.3	Rescue Medications	Enrolled Subjects	
16.2.9.4	Procedures	Enrolled Subjects	
16.2.9.5	Sheehan-Suicidality Tracking Scale Results	Enrolled Subjects	

Figure Number	Title	Population	Topline
14.2.1	Forest Plot of Pain Freedom at 2 Hours Post Dose	mITT Subjects	
14.2.1.1	Forest Plot of Pain Freedom at 2 Hours Post Dose: Sensitivity Analysis 1	mITT Subjects	

14.2.1.2	Forest Plot of Pain Freedom at 2 Hours Post Dose: Sensitivity Analysis 2	mITT Subjects	
14.2.1.3	Forest Plot of Pain Freedom at 2 Hours Post Dose: Sensitivity Analysis 3	mITT Subjects	
14.2.1.4	Forest Plot of Pain Freedom at 2 Hours Post Dose: Sensitivity Analysis 4	mITT Subjects	
14.2.1.5	Forest Plot of Pain Freedom at 2 Hours Post Dose by Subgroup	mITT Subjects	
14.2.2	Forest Plot of Freedom from Most Bothersome Symptom at 2 Hours Post Dose	mITT Subjects	
14.2.2.1	Forest Plot of Freedom from Most Bothersome Symptom at 2 Hours Post Dose: Sensitivity Analysis 1	mITT Subjects	

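### Non-liver laboratory tests: objective 7 is partly reported, but no planned table gives a judgement-free count by arm of markedly abnormal values

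*SAP*

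**What the plan says.** SAP 1.2.3, objective 7, names among its safety measures the frequency of "serious adverse events, and clinically relevant laboratory abnormalities". Nothing there limits this to liver tests, and no numeric limit or grade is given. Protocol 1.2.4 identifies liver function as the primary AE of interest, then adds: "Clinicians should also monitor changes in hematology and other laboratory measures".

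For laboratory tests in general, SAP 4.9.3 compares the end-of-treatment visit with baseline as follows: "shift from baseline in laboratory tests will be summarized as the number and percentage of subjects with each category (low, normal, high"). Appendix 1 carries this out in shift tables for hematology, chemistry ("Serum Chemistry: Shift from Baseline by Visit") and urinalysis. Where a post-baseline visit has repeats, the value nearest the target date is used, and the later record breaks a tie. SAP 4.9.3 also plans observed and change-from-baseline summaries for select continuous parameters. Abnormal values are listed by subject, for example in the listing "All Abnormal Laboratory Results (SI Units").

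Protocol 8.2.2 sends certain results to the AE or SAE forms: those that are clinically significant, those that led to interruption or discontinuation, and "Any laboratory abnormality that required the subject to receive specific corrective therapy".

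Liver tests get more. AST and ALT shifts are graded by multiples of the upper limit of normal (ULN) in Table 14.4.6. For Table 14.4.7, "a table will be created that summarizes the on-study incidence (as the number and percentage of subjects with an elevation") past stated cut-offs. For the eDISH plot, "The maximum values for each subject during the study will be identified as the maximum values that occur on study".

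**The concern.** A low/normal/high cell puts a value just outside the reference range together with a grossly abnormal one. The cell counts out-of-range subjects, which is a wider group than those with a clinically relevant change. The AE tables come closer to clinical relevance, but entry depends on each investigator's view, and no table separates laboratory AEs from the rest. For hematology, CK and renal function a reader of the report would therefore have a loose upper count and a site-dependent count, with nothing objective between them.

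The repeat rule adds a smaller problem. A marked result is the kind most likely to be repeated. If the repeat falls nearer the target (dose + 7 days in SAP Table 6) and is normal, the shift table shows only the normal value. The marked one remains in the listings and may be recorded as an AE.

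At stake is whether a small excess of marked values in one arm can be seen in a summary table, or only by working through listings.

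**Working it through.** There is no stated figure to reproduce. The check is an inventory of planned outputs, followed by an illustration.

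**Inventory for non-liver tests (SAP 4.9.2, 4.9.3 and Appendix 1; Protocol 8.2.2)**

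| Output | What it counts or shows | Marked values counted by arm? |
|---|---|---|
| Shift Tables 14.4.3, 14.4.4, 14.4.5, 14.4.5.2 | Subjects by reference-range category | No; slight and marked values share a cell |
| Observed and change Tables 14.4.1.1 to 14.4.2.2 | Mean, median, SD, minimum and maximum for select parameters | No; extremes, not numbers of subjects |
| AE Tables 14.3.2.1 to 14.3.2.6 | Subjects by arm and preferred term | Only through investigator judgement |
| Listings 16.2.8.x | Individual values | No; not summarised |

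Appendix 4 adds no laboratory table. The liver incidence table in SAP 4.9.3.1 has these rows: 4 multiples × 3 (AST, ALT, either) = 12, plus 2 for bilirubin, 1 for ALP, 2 for transaminase with bilirubin and 1 for transaminase with symptoms, so 18. Non-liver tests have 0. This contrast describes layout; it does not measure harm.

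**Illustration of dilution**

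Input from the documents: about 600 treated per arm (Protocol 9.2). Assumptions not in the documents: 6 subjects on rimegepant and 0 on placebo with a marked value, and a mildly out-of-range rate of 1% to 10%, equal in both arms.

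The interval is Newcombe's. Each arm has Wilson limits (p + z²/2n ± z√(p(1−p)/n + z²/4n²)) / (1 + z²/n). With d = p₁ − p₂, the lower limit is d − √((p₁−l₁)² + (u₂−p₂)²) and the upper limit is d + √((u₁−p₁)² + (p₂−l₂)²).

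For 6 against 0, in percent: p₁ = 1.000 (0.459 to 2.164) and p₂ = 0 (0 to 0.636). Lower: 1.000 − √(0.541² + 0.636²) = 0.16 with unrounded limits. Upper: 1.000 + 1.164 = 2.16.

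| Display | Rimegepant vs placebo | Difference, points (95% CI) | Marked share of rimegepant cell |
|---|---|---|---|
| Threshold table | 6 vs 0 | 1.0 (0.16 to 2.16) | 100% |
| Shift cell, mild 1% | 12 vs 6 | 1.0 (−0.44 to 2.56) | 6/12 = 50% |
| Shift cell, mild 2.5% | 21 vs 15 | 1.0 (−0.99 to 3.04) | 6/21 = 29% |
| Shift cell, mild 5% | 36 vs 30 | 1.0 (−1.62 to 3.64) | 6/36 = 17% |
| Shift cell, mild 10% | 66 vs 60 | 1.0 (−2.49 to 4.50) | 6/66 = 9% |

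The exclusion of zero in the first row depends on the chosen split: 6 vs 1 gives −0.11 to 2.01, and 4 vs 0 gives −0.09 to 1.70. The falling share in the last column does not depend on whether an interval excludes zero.

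**The case against.** The strongest reply is that objective 7 is already answered on the protocol's own terms. Neither document equates clinical relevance with a numeric limit, and the inclusion criteria in Protocol 5.2 leave the significance of an out-of-range result to the investigator. Protocol 8.2.2 then requires significant results to be recorded as AEs or SAEs, which SAP 4.9.2 counts by arm. A reader might infer from the missing threshold table that the objective goes unreported for non-liver tests. The documents do not support that, and this part of the reply stands.

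Other points also stand in part:

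- The minimum and maximum in the observed and change tables would show a gross outlier for any selected parameter, though not how many subjects had one.
- The liver emphasis is deliberate. Protocol 9.4.3 promises displays for liver tests, and the remark about hematology in 1.2.4 is guidance for clinicians, not a promised table.
- The shift tables arguably meet the rule in Protocol 9.1 that laboratory abnormalities are counted by unique subjects.
- The repeat problem is narrow. Protocol Table 1 schedules one post-dose laboratory draw, and the rule applies only to repeats from that visit.
- Any cut-offs would be new choices. The neutrophil and eGFR limits proposed below are entry criteria, not outcome definitions.

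None of this supplies a count by arm that is independent of site judgement. Two sites with the same laboratory value may differ on whether it becomes an AE, and the shift cell cannot separate it from a trivial deviation.

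**Conclusion.** The point holds as a minor, inexpensive improvement. Shifts, summaries, listings and AE counts report objective 7 in part. The gap is one objective count of markedly abnormal non-liver values by arm, together with a narrow route by which a marked value can leave the shift table after a normal repeat.

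The absence of such a table is certain from SAP 4.9.3 and the appendices. Its consequence is modest: a single-dose trial, an exploratory objective, liver as the main safety interest, and every abnormal value listed.

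The 6 against 0 figures should not be read as an expected effect or as evidence of a hidden signal. They rest on assumed counts and assumed mild rates, and show only that the larger the mild group, the smaller the part of the cell that marked values occupy.

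**What to change.** Add one descriptive table for treated subjects by arm, modelled on Table 14.4.7 and without p-values. Give the number and percentage whose worst on-treatment value, repeats included, passes cut-offs written into the SAP before unblinding. The denominator for each test is subjects with at least one on-treatment value for it. Suggested cut-offs:

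- Neutrophils ≤1000/µL and eGFR ≤40 mL/min/1.73m², the exclusion limits in Protocol 5.3. An eligible subject was above both at screening, so a later value there is new.
- CK >5x and >10x ULN, multiples that SAP 4.9.3.1 already uses for AST and ALT.
- Other tests, such as hemoglobin, platelets, creatinine and electrolytes, by one grading scale named with its version. The documents give no limits for these, so the choice is the sponsor's.

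Keep the shift tables, summaries and listings as planned.

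The cost is one SAP paragraph, one table and agreement on cut-offs; the central laboratory already supplies the data. Most cells are likely to be small or zero, and with several rows some chance imbalance between arms should be expected. That is why the table should stay descriptive.

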4.2 Study Schematic

4.3 Schedule of Assessments

Table 1: Schedule of Assessments

| Procedure | Screening Visit (3-28 days)¹ | Baseline Visit (Randomization)¹ | Onset of moderate or severe migraine² | During Treatment 15, 30, 45, 60 and 90 minutes Post-Dose | During Treatment 2, 3, 4, 6, 8 hours Post- Dose | During Treatment 24 hours Post-Dose | During Treatment 48 hours Post- Dose | End of Treatment Visit (within 7 days of migraine)¹⁵ |
|--|--|---|---|---|--|--|---|--|
| Eligibility Assessments | | | | | | | | |
| Informed Consent | X | | | | | | | |
| Inclusion/Exclusion Criteria | X | X | | | | | | |
| Medical History | X | | | | | | | |
| Prophylactic Migraine Medication/ Concomitant Medication ³ | X | X | | | | | | X |
| Assessment of Migraine History (Signs and symptoms) paper source ¹⁴ | X | | | | | | | |

| Procedure | Screening Visit (3-28 days)¹ | Baseline Visit (Randomization)¹ | Onset of moderate or severe migraine² | During Treatment 15, 30, 45, 60 and 90 minutes Post-Dose | During Treatment 2, 3, 4, 6, 8 hours Post-Dose | During Treatment 24 hours Post-Dose | During Treatment 48 hours Post-Dose | End of Treatment Visit (within 7 days of migraine)¹⁵ |
|---|--|---|---|---|---|--|--|--|
| Safety Assessments | | | | | | | | |
| Physical Examination | X | | | | | | | X |
| Vital Signs/Physical Measurements ⁴ | X | X | | | | | | X |
| Clinical Safety Laboratory Testing ⁵ | X | | | | | | | X |
| Urine drug screen for drugs of abuse | X | | | | | | | X |
| ECG | X | | | | | | | X |
| Pregnancy Test ⁶ | X | X | X | | | | | X |
| Adverse Event and Serious Adverse Event Assessment ⁷ | X | X | X | X | X | X | X | X |
| Sheehan Suicidality Tracking Scale ⁸ | X | X | | | | | | X |

| Procedure | Screening Visit (3-28 days)¹ | Baseline Visit (Randomization)¹ | Onset of moderate or severe migraine² | During Treatment 15, 30, 45, 60 and 90 minutes Post-Dose | During Treatment 2, 3, 4, 6, 8 hours Post-Dose | During Treatment 24 hours Post-Dose | During Treatment 48 hours Post-Dose | End of Treatment Visit (within 7 days of migraine)¹⁵ |
|---|--|---|---|---|---|--|--|--|
| Efficacy Assessments¹² | | | | | | | | |
| Assessment of migraine pain ¹³ | | | X | X | X | X | X | |

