⁷ SAEs are reported from the time of informed consent and non-serious AEs are reported from baseline. All ongoing non-serious AEs and SAEs will be followed to resolution or until investigator deems there will be no further status change. SAEs that occur during the treatment period should be reported to site in real time. Non-serious AEs that occur during the treatment period should be reported to the site at the EOT.

⁸ This scale will be clinician administered, completed on site, and will be in paper. The source document will be provided by Biohaven. The assessment period for completing the scale will be 30 days prior to Screening, and since the last visit for the remainder of the study.

⁹ Subjects will be randomized in the IWRS system at the Baseline Visit (Randomization Day 01).

¹⁰ Subjects should be instructed that the dose should be taken once the migraine attack reaches moderate or severe pain and after the subject has completed all required migraine assessments in the eDiary. The eDiary will prompt the subject to take study medication.

¹¹ Site staff to review and confirm entries with subjects and confirm all data points are transferred to the system and reset eDiary for future subject use, PRIOR to the subject leaving the clinic.

¹² ± Windows for timeframe around efficacy assessments (15, 30, 45, 60, 90 min, 2, 3, 4, 6, 8, 24 and 48 hours) will be automated and captured in the eDiary.

¹³ These scales will be captured in the eDiary. Subjects will also be asked about their most bothersome symptom at the time of reporting and treating a qualifying migraine.

¹⁴ Paper source document will be used to capture Migraine History. Subjects will also be asked about their typical most bothersome symptom when having a migraine.

¹⁵ Subjects should return to the site for their EOT visit within 7 (+2) days from their migraine occurring.

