4.3.2 Acute (Randomization) Phase (45 days)

If the subject meets all eligibility criteria they will be randomized at the Baseline Visit via the IWRS. The subjects will be provided with an eDiary. The study personnel will instruct the subject on the proper use of the eDiary and ensure proper understanding and use of the tool, prior to the subject leaving the office.

After randomization via the IWRS, the subject will be dispensed a single dose of the double-blind study medication to take home for up to 45 days. This study medication is to be taken when a migraine attack reaches moderate or severe intensity on the numeric rating scale (NRS) as indicated in the eDiary. The subject will be instructed to take their study medication, as an outpatient, when (if) they have a migraine headache which reaches moderate or severe intensity **after they answer eDiary questions about their current pain and symptoms and identify their currently most bothersome, migraine associated, symptom (phonophobia, photophobia or nausea)**. The subject will complete an eDiary for forty-eight hours after taking study medication to record efficacy and other quality of life measures.

Subjects in this study may be randomized only once. Under no circumstances may a subject be re-randomized.

4.3.2.1 eDiary Data Collection

Subjects will record efficacy and other quality of life measures in their eDiary. This includes the following: onset time of headache, intensity of the headache prior to and at time of taking study medication. The subjects should not dose with study medication until the headache reaches moderate or severe intensity. Headache severity will be recorded using a four-point numeric rating scale (no pain, mild pain, moderate pain, severe pain) at the onset of the migraine and after dosing at time points of 15, 30, 45, 60, and 90 minutes and 2, 3, 4, 6, 8, 24 and 48 hours. The presence or absence of associated symptoms (nausea, photophobia, phonophobia) and ratings of functional disability (four-point scale: normal, mildly impaired, severely impaired, requires bedrest) will be recorded at the same time points as the headache severity ratings. Subjects will also identify their currently most bothersome symptom before

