4.9.2 Adverse Events

AEs will be coded using MedDRA and displayed in tables and listings by SOC and PT, unless specified otherwise.

On-study AEs are those with a start (onset) date on or after the randomization date.

Adverse events are summarized by subject incidence rates; therefore, in any tabulation, a subject contributes only once to the count for a given AE (SOC or PT). The number and percentage of subjects with any on-study AE, with any on-study AE related to treatment (unlikely related, possibly related, or related), with any on-study SAE, with any on-study SAE related to treatment, with any on-study severe AE, with any on-study AE leading to study drug discontinuation and with any on-study AE leading to death will be summarized by treatment group and overall.

The number and percentage of subjects with on-study AEs will also be summarized by SOC and PT for the following: any AE; AEs related to study drug; SAEs; severe AEs; and AEs leading to study drug discontinuation. AEs will be displayed in descending order of overall frequency within SOC and PT.

In these tabulations, each subject will contribute only once (i.e., the most related occurrence or the most intense occurrence) to each of the incidence rates in the descriptive analysis, regardless of the number of episodes. All AEs will be listed and indicate whether or not the AE was serious, occurred on study, or potentially occurred on treatment. Additional listings will be provided including: deaths; SAEs; and AEs leading to study drug discontinuation.

Potentially on-treatment AEs are those with a start date on or after the first dose of study drug date. Given that the AEs do not have recorded onset times, these on-study events are considered to be potentially on-treatment. (Thus, potentially on-treatment AEs are a subset of on-study AEs).

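### One descriptive row of the liver table can pair a post-dose AST/ALT value with a symptom that was over before the single dose

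*SAP*

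**What the plan says.** SAP 4.9.3.1 (within 4.9.3 Laboratory Data) lists the rows of a table of on-study liver findings. Appendix 1 gives it as Table 14.4.7, in treated subjects and marked as topline. The last row is "Elevation of AST or ALT along with an on-study AE of nausea, vomiting, anorexia, abdominal pain, or fatigue". It sets no condition on when the symptom occurs relative to the dose or the blood sample.

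The timing terms are defined nearby:

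- SAP 4.9.2: "On-study AEs are those with a start (onset) date on or after the randomization date".
- SAP 4.9.2 also has a dose-anchored class: "Potentially on-treatment AEs are those with a start date on or after the first dose of study drug date". Events on the dosing day belong to it: "Given that the AEs do not have recorded onset times, these on-study events are considered to be potentially on-treatment". The SAP uses this class as a flag in the AE listing, not in this row.
- SAP 4.9.3: "On-treatment laboratory values are those with collection date/time after the first dose of study drug date/time". On-study values need only follow randomization.

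The protocol fixes the calendar:

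- Section 4.3.2: after randomization, "the subject will be dispensed a single dose of the double-blind study medication to take home for up to 45 days".
- Table 1, footnote 7: "SAEs are reported from the time of informed consent and non-serious AEs are reported from baseline".
- Table 1 marks "Clinical Safety Laboratory Testing" at Screening and End of Treatment only. Section 4.3.4 places End of Treatment within 7 (+2) days after treatment.

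**The concern.** The row is meant to show transaminase elevations accompanied by symptoms that might point to the liver. The protocol (1.2.4) names change in liver function tests as the main AE of interest, so a reader will look at this row and will naturally take both halves as following the drug. The definitions do not ensure that. A subject with a day of nausea in the second week, a dose in the fourth week and a slightly raised ALT at End of Treatment is counted, although the nausea ended before exposure and says nothing about the drug. What is at stake is the meaning of one count in a topline safety table.

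**Working it through.** The documents state no figure for this row, so there is none to reproduce. The check has two parts.

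**1. Timing of the two halves in a treated subject on schedule**

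| Element | Earliest | Latest |
|---|---|---|
| Start of an on-study AE | randomization date | End of Treatment |
| Dose | randomization | 45 days later |
| Scheduled on-study AST/ALT | End of Treatment, after the dose | 9 days after the dose |

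No safety laboratory sample is scheduled at Baseline or between Baseline and End of Treatment. For the laboratory-only rows, on-study and on-treatment therefore coincide by schedule. They differ only in this row, because only this row brings in AEs. An unscheduled sample before the dose would be an exception.

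**2. Size**

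Inputs from the documents:

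- 2 to 8 moderate or severe attacks per month (protocol 5.2), so an average spacing of 30/8 = 3.75 to 30/2 = 15 days.
- F = 7 or 9 days from dose to End of Treatment.
- 600 treated subjects per arm (protocol 9.2, SAP 4.1).

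Assumptions, not in the documents: the first attack is treated; background AEs occur at a constant rate; a symptom lasts L = 1 to 3 days; 2% to 5% of subjects have AST or ALT above ULN at End of Treatment; 2% to 4% have one of the five AEs; the two are independent.

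Let D be the days from randomization to dose.

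*Share of the on-study AE window before the dose* = E[D] / (E[D] + F).

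- Evenly spaced attacks, mean wait half the spacing: 1.875/(1.875 + 9) = 17.2% to 7.5/(7.5 + 7) = 51.7%.
- Memoryless attacks, mean wait the full spacing: 3.75/(3.75 + 9) = 29.4% to 15/(15 + 7) = 68.2%.

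*Share also resolved before the dose* = E[(D − L)+] / (E[D] + F). This is the share that matters here.

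- Lowest: evenly spaced, spacing 3.75, L = 3, F = 9. E[(D − 3)+] = 0.75²/(2 × 3.75) = 0.075, and 0.075/10.875 = 0.7%.
- Highest: memoryless, mean 15, L = 1, F = 7. E[(D − 1)+] = 15 × exp(−1/15) = 14.03, and 14.03/22 = 63.8%. Restricting to doses by Day 45 gives E[D] = 12.64, E[(D − 1)+] = 11.68 and 11.68/19.64 = 59%.

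*Chance pairs per arm*: 600 × 2% × 2% = 0.24 to 600 × 5% × 4% = 1.2.

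*Pairs whose symptom resolved before the dose*: 0.24 × 0.007 = 0.002 to 1.2 × 0.638 = 0.77.

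**Sensitivity**

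- The plan expects roughly 85% to have a migraine in the window. Under the memoryless model that implies a mean wait of 45/(−ln 0.15) = 23.7 days, or 15.8 days among those dosed by Day 45. The resolved share for L = 1, F = 7 becomes 14.80/(15.8 + 7) = 65%, and 1.2 × 0.65 = 0.78.
- A deliberately wide case, 8% with an elevation and 6% with a symptom, gives 600 × 8% × 6% = 2.88 pairs, of which 2.88 × 0.007 = 0.02 to 2.88 × 0.638 = 1.84 resolved before the dose.

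**The case against.** The strongest reply is that this is a convention, not a slip. The AE tables, the liver table and the eDISH plot are all anchored to randomization, and SAP 4.2.7 describes its handling of incomplete AE dates as worst case. The listings flag which AEs and laboratory values are on treatment, so with about one pair per arm each case can be classified by hand. No test, alpha or stopping rule uses the row.

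Most of this stands, and it limits the weight of the point. The convention does not settle it, however, because it is harmless in the laboratory-only rows and changes the meaning only here. Listing flags help a careful reader but leave the topline count unchanged.

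Three further points are fair:

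- Moving the row wholly to AEs that start on or after the dose date would drop symptoms that began earlier and were still present at dosing. That removes more than the defect and loses sensitivity.
- Requiring on-treatment laboratory values in this row would change nothing on schedule.
- SAP 4.2.7 compares incomplete AE dates with randomization only, so a dose-anchored row needs a date rule the SAP does not yet have.

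The size model is also soft. No visit is scheduled between Baseline and End of Treatment, so short early symptoms may be under-recalled, which would lower the shares. Leaving the first qualifying attack untreated, which protocol 4.3.2.1 allows for, would raise them.

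**Conclusion.** The point holds as a minor one. The row's definition admits symptoms that started and resolved between randomization and the dose, next to a liver value that by schedule is post-dose. The expected effect is probably under one subject per arm, on assumed event rates and independence, and just under two in the wide case. Under blinding it should be balanced between arms, so it adds non-drug counts to both.

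A reader might infer more than the documents support:

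- *That the plan would report false liver toxicity or favour an arm.* The row is descriptive, and the multiple-of-ULN rows, the Hy's Law criteria and the eDISH plot do not depend on AE timing.
- *That most of the AE window lies before the dose.* A share of 45/(45 + 9) = 83% to 45/(45 + 7) = 87% applies only to a dose on Day 45. The documents give no distribution of time to dose.
- *That every symptom starting before the dose is miscounted.* One still present at dosing can reasonably stay in the row.
- *That the unstated AST/ALT cut in this row is part of the error.* Stating it would be a useful clarification, but it is a separate matter.

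**What to change.** In this row, count only listed on-study AEs that are potentially on-treatment (start date on or after the dose date) or were still ongoing on the dose date. Extend the worst-case rule of SAP 4.2.7 to match: keep an AE with a partial or missing date unless it definitively ended before the dose date. Add a footnote that this row is dose-anchored while the rest of the table is on-study. No further window between symptom and sample is needed, since the sample is due within 7 (+2) days of the dose.

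The cost is a line or two of SAP wording, one footnote and one extra date rule to program. The potentially on-treatment flag already exists for the listings. The downside is that one row departs from the table's on-study label, which the footnote explains.
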